2. OBJECTIVES OF THE STUDY

The objective of the study is to investigate the correlation between the levels of HbF and the use of umbilical cord blood red cell concentrate transfusions in ELBW preterm infants and/or infants who were born before the 30th week of gestational age (GA). Since transfusions are one of the main mechanisms to reduce HbF, they will be carried out with umbilical cord blood red cell concentrates (UCB-RBC). Our objective is to demonstrate that UCB-RBC transfusions, until the 32nd week of PMA, guarantee average levels of HbF that are higher than in adult-RBC (A-RBC) transfusions. The following outcomes were defined:

Primary outcome:

- Average levels of HbF at 32nd week of PMA in patients receiving different transfusion support.

Secondary outcomes:

- To show that UCB-RBC transfusions are not less effective than A-RBC transfusions, as for the post-transfusion increase in the hematocrit and the interval between two transfusions.
- To show the association between average levels of HbF during the inpatient stay and comorbidities (ROP, BPD, NEC, PVL and IVH) or deaths occurred within 36 weeks of PMA.

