3. EXPERIMENTAL DESIGN

3.1 Study design. This study is a prospective non-randomized study to evaluate the correlation between the reduction in the level of HbF (based on the relation between HbF and HbA) before the 36th week of PMA and the type of transfusion (UCB-RBC or A-RBC).

3.2 Duration of the study. The study will have an overall duration of one year. The enrollment of patients will last 10 months. Considering the volume of activity of our NICU and the type of eligible patients, such a period of time was considered adequate to enroll the number of patients necessary to reach the established objectives. As for the transfusions (UCB-RBC or A-RBC), the intervention phase will last from the enrollment to the completion of the 32nd week of PMA, while the weekly monitoring of HbF will continue until the completion of the 36th week of PMA.

3.3 Early study termination. The study will be terminated with the occurrence of adverse events that can be risky for the patients or if the Proposer thinks it is necessary, based on the evaluation of safety data.

3.4 Study termination. The study will be considered over when the collected data make it possible to draw up the final report.

3.5 Study endpoints.

- HbF levels before and after each transfusion;
- Average HbF levels (at 32 weeks of PMA; at last control)
- Prevalence of ROP and/or BPD and/or NEC and whatever health problems (infectious pathologies, hemorrhages including IVH, kidney failure, thromboembolism, surgical complications, etc.) before the 36th week of PMA;
- Transfusion efficacy of UCB-RBC compared to A-RBC (all transfusions before the 36th week of PMA, evaluated based on a) average time interval between two subsequent transfusions and b) average increase in the post-transfusion capillary hematocrit (Δ Hct).

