5. PROCEDURES

5.1 Enrollment. Cord blood donors will be enrolled according to the procedures implemented by the bank personnel of the UNICATT Cord Blood Bank. The medical personnel of the Neonatology ward will enroll patients when they are hospitalized in the NICU. The parents/tutors of the newborns who meet the inclusion criteria will be adequately informed about the study and will be asked to give their informed consent (Annex I and Annex I bis). Researchers will provide exhaustive information both on the aim of the study and the related procedures. Investigators will be in charge of providing all the necessary information, including that on the parents' right to withdraw their consent to participate in the study whenever they want and for whatever reason without affecting the newborn's treatment. A copy of the consent shall be provided to the parents/tutors and the researchers will keep another. Only the newborns whose parents have given their consent can be enrolled.

5.2 Enrollment communication to the Blood Transfusion Service. Once parents/tutors have given their informed consent, the researchers of the NICU will communicate the patient's

name to the Blood Transfusion Service. The researchers of the Blood Transfusion Service will keep an up-to-date list of the enrolled patients by reporting:

- date of the completion of the 32nd week of PMA (termination of A-RBC intervention phase);
- date of the completion of the 36th week of PMA (study termination).

5.3 Description of the blood component Umbilical Cord Blood red cell concentrates. The study will be based on the transfusion of umbilical cord blood units taken from the pregnant women who are part of the Cord Blood Bank donors and who gave their informed consent on the use of the donated unit for research purposes.

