5.4 The collection of cord blood will be carried out in the birth centers that are part of the Cord Blood Bank, according to the procedures used by the Bank itself. The collected units will be adequately conserved at low temperatures (2-6°C) and fractionated within 24 hours. The units that are not eligible for transplant because of low cellularity (total nucleated cells <1,200 x 10⁶), with a volume >60 ml excluding the anticoagulant (CPD, Citrate, Phosphate, Dextrose), without clots and/or hemolysis, will be considered eligible for fractionation to obtain UCB-RBC. Eligible UCB units will be fractionated by an automatic blood component processing system (the UNICATT Cord Blood bankl will use Compomat[®] G4 by Fresenius HemoCare GmbH, D-61346, Bad Homburg, Germany). Red cell concentrates will be resuspended in a preservative solution containing adenosine, glucose and mannitol (SAGM, ratio red cell: SAGM = 2:1) and filtered with the filter Purecell[®] NEO Neonatal High Efficiency Leukocyte Reduction Filter (Pall, East Hills, NY, USA) to remove leukocytes. Blood cultures for bacteria and fungi will be set up. Only the units that tested microbiologically negative will be considered eligible for transfusion (blood cultures, molecular and serological tests for HCV, HBV, HIV and syphilis). UCB-RBC units will be stored at a temperature of 2-6°C for 14 days, in order to allow the γ -irradiation (¹³⁷Cs) when they are assigned to the patient.

5.5 Transfusion request. Units will be requested according to the procedures established by the Blood Transfusion Service, based on the current legislation and in accordance with the guidelines reported in Annex III. When a blood request arrives, the hematologist on duty at the Blood Transfusion Service will check if the patient's name is included among those enrolled in the study and the date of completion of the 32nd week of PMA; then he/ she will identify ABO-Rh(D) units to transfuse (UCB-RBC if available, otherwise A-RBC). The transfusion dose will be determined regardless of the type of blood component being used and will be established according to the criteria generally implemented in the NICU. The UCB-

RBC and A-RBC units will be transfused within six hours in order to reduce functional alterations of red cells and the risk of microbial contamination.

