6. STATISTICAL CONSIDERATIONS

6.1 Definition of analysis sets

- **Enrolled (E) set or Intent-to-treat (ITT) analysis.** It will comprise all the enrolled patients, regardless of the administration or not of RBC transfusions.
- **Treated (T) set.** This group will comprise all the patients who were at least administered one transfusion, regardless of the completion of the observation period (36th week of PMA). Excluded from this set are the enrolled patients who were not transfused.
- **Per-Protocol (PP) set.** This group will comprise all the transfused patients who completed the observation period (36th week of PMA) or who died after completing it.

6.2 Calculation of sample size. The main goal of the study is to correlate the average HbF levels to the type of transfusion (UCB-RBC or A-RBC). With a population of 25 patients that will be studied during the following 8 weeks and a mortality rate of 1.9 patients/month, we expect to have 196 weekly doses of HbF to correlate to 98 transfusions. The total expected number of transfusion from birth to the completion of the 36th week of PMA was calculated to be around four transfusions per patient, with an UCB-RBC:A-RBC ratio of 1:1. In fact, for those patients with birth-determined characteristics similar to those of the studied population, the average number of transfusions within the 36th week of PMA is around 4 transfusions/patient [25], while in our previous study the average number of transfusions was 3 ± 1.7 [46]. In accordance with the literary data, preterm infants have an expected HbF concentration between 85% and 90% at birth and between 70% and 75% at the 36th week of PMA [54]. We expect that for the newborns who will not be transfused the HbF levels will stay in this range (70%-90%), while for the patients who will be transfused with adult red cells, HbA will dilute HbF. Even though there are no literary data yet, if we know the volume of transfused red cells (20 ml/kg) and the patient's blood volume, we can also assume that, for every adult red cell transfusion, HbF will be reduced by 15-20% compared to the pre-transfusion values until reaching levels lower than 20% among those patients who were transfused more than 4 times with adult blood.

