6.3 Statistical data analysis. The continuous variables will be expressed as mean (\pm SD) or as median (interquartile ranges, IQR); all deviations from normality will be detected with the Shapiro-Wilk test. The categorical variables will be expressed as n, (%), percentage). HbF levels in different type of transfusions will be compared in univariate analysis Mann-Whitney U test, end Kruskall Wallis test). Similarly, the transfusion efficacy analysis will be carried out based on a UCB-RBC and A-RBC non-inferiority study design by comparing the average time interval between two subsequent transfusions and the average post-transfusion capillary Ht

increase (Δ Ht) (Mann-Whitney U Test). The transfusion sample included in the study makes it possible to detect a difference between groups that is equal to at least 1 standard deviation with type I error $\alpha = 0.05$ and type II error $\beta = 0.2$ and a medium effect size (0.6). The correlation between the type of transfusion and other variables (prematurity related pathologies) will be tested using Fisher's exact test. Secondarily, in order to evaluate the effect of HbF reduction on the onset of prematurity-related pathologies, the levels of HbF levels will be inserted in a multiple linear regression model, by expressing the correlation between the onset of prematurity-related pathologies and the variables in terms of odds ratios (ORs \pm 90% confidence interval).

6.4 The primary outcome analysis will be tested on "E", "T" and "PP" sets. Transfusion efficacy outcome will be tested on "T" and "PP" sets.

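### Transfusion efficacy to 36 weeks PMA is tested with no infant or PMA term, although the intervention phase ends at 32 weeks and the plan does not say what changes then

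*Combined protocol and SAP*

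**What the plan says.** Section 3.5 defines the efficacy comparison over "all transfusions before the 36th week of PMA, evaluated based on" the interval between consecutive transfusions and the capillary haematocrit rise. Section 6.3 describes it as a "non-inferiority study design by comparing the average time interval between two subsequent transfusions" and the haematocrit rise, each by Mann-Whitney test. It names no margin, no covariate and no term for the infant.

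The sections treat 32 weeks PMA differently:

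- Section 3.2, naming both products: "the intervention phase will last from the enrollment to the completion of the 32nd week of PMA". Weekly HbF monitoring goes on to 36 weeks.
- Section 2 states the aim as showing that "UCB-RBC transfusions, until the 32nd week of PMA, guarantee average levels of HbF" above those seen with adult units.
- Section 5.2 keeps on the enrolment list the "date of the completion of the 32nd week of PMA (termination of A-RBC intervention phase", which names only the adult product.
- Section 5.5 has the haematologist check "the date of completion of the 32nd week of PMA" before choosing a unit. A cord unit is used when one is in stock, and an adult unit if not. No separate rule is given for requests after that date.
- Section 6.2 counts "The total expected number of transfusion from birth to the completion of the 36th week of PMA" and puts it at "around four transfusions per patient, with an UCB-RBC:A-RBC ratio of 1:1".

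**The concern.** There are two separate problems.

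The first does not depend on the 32-week boundary. Each infant contributes about four transfusions, and transfusions in the same infant are likely to resemble one another. A Mann-Whitney test on pooled transfusions ignores this, so its p-values, and any confidence interval built the same way, are not valid.

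The second is conditional. Product is not randomised, and a date that is listed and checked before each unit is chosen presumably affects the choice. If the mix of cord and adult units changes at 32 weeks, late transfusions are over-represented in one product. Any difference in haematocrit rise or interval between early and late transfusions would then be read partly as a product effect, within a comparison meant to show that cord units are no worse.

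**Working it through.** **Inputs from the documents.** Section 6.2 gives 98 transfusions, about four per infant, at 1:1. So 98 / 4 = 24.5 infants and 98 / 2 = 49 transfusions per product. Section 6.3 gives α = 0.05, β = 0.2 and effect size 0.6.

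**Inputs not in the documents (assumed).** These are f, the share of transfusions given after 32 weeks; d, the early-late difference in the outcome, taken as 0.25-0.5 SD; and all late transfusions being of one product. On f, section 1 says only that ELBW infants receive most of their transfusions before 32 weeks.

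**The plan's own figure.** With 49 v 49 independent transfusions, the SE is √(2/49) = 0.202 SD. Two-sided power at 0.6 SD is Φ(0.6/0.202 − 1.96) = 0.84, and 0.83 after allowing for the Mann-Whitney efficiency of 0.955 under normality. The stated 80% at 0.6 is therefore roughly reproduced, but only if transfusions are independent. (The 1 SD in the same sentence is a different target, needing only 16 per group.) The 95% half-width is 1.96 × 0.202 = 0.40 SD.

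**Independence.** Let ρ be the within-infant correlation, with four transfusions per infant. The variance of the product difference, relative to independence, is:

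- 1 + 3ρ if each infant receives only one product, so the test overstates precision;
- 1 − ρ if each infant receives two of each, so the test understates precision.

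Availability-based choice can give anything between. The standard error is wrong whenever these effects do not happen to cancel, and the direction cannot be fixed in advance.

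**Confounding with PMA, haematocrit rise.** Spurious difference = (late share within the affected product) × d. The other product has no late transfusions.

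| Scenario | Late share of affected product | d = 0.25 | d = 0.5 |
|---|---|---|---|
| No change of mix at 32 weeks | equal in both | 0 | 0 |
| f = 10%, 1:1 before 32 weeks | 2f/(1+f) = 0.2/1.1 = 0.182 | 0.05 SD | 0.09 SD |
| f = 20%, 1:1 overall to 36 weeks | f/0.5 = 2f = 0.40 | 0.10 SD | 0.20 SD |

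The second row gives 44.1 v 53.9 transfusions (45:55). The third gives 49 v 49, which meets the ratio in section 6.2 exactly.

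A simulation of the two-sided Mann-Whitney test (98 independent transfusions, no true product effect, 4,000 runs, d = 0.5) gave false-positive rates of 0.07 in the second row and 0.16 in the third. With no change of mix (20-30% late, a 1 SD shift) the rate was 0.03. These are rates for a test of difference. The rate of false non-inferiority cannot be computed without a margin.

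**Intervals.** An infant's last transfusion starts no interval, so 98 − 24.5 = 73.5 remain. Suppose each interval is credited to the product that starts it, which the plan does not say, and the mix is 1:1 before 32 weeks. At f = 10% the spurious difference is then 0 to 0.08 SD, depending on how many late transfusions each affected infant has.

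**Would restricting to 32 weeks be better as the main analysis?** At f = 10% with 1:1 before 32 weeks:

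- Pooled variance: 1/44.1 + 1/53.9 = 0.0412.
- Restricted variance: 2/44.1 = 0.0454.
- The increase of 0.0041 exceeds the squared bias (0.182d)² whenever d is below about 0.35 SD.

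Restriction therefore raises mean squared error for small d. Power at 0.6 SD goes from 0.84 to 0.80.

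**The case against.** The strongest reply is that the confounding is hypothetical. The only selection rule, in section 5.5, carries no stated time limit, and section 6.2 plans 1:1 over the whole period to 36 weeks. No section says that the mix changes. Nor does any source in the plan support an early-late difference of 0.25-0.5 SD. For haematocrit rise in particular, section 6.2 assumes a weight-scaled volume and section 5.5 sets the dose without regard to product. This stands: the text shows an unresolved inconsistency and an analysis with no protection against it, not a demonstrated bias.

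It also stands that the 36-week window is used consistently in sections 3.5, 5.6 and 6.2, and that cutting the main comparison at 32 weeks costs precision. That argues for keeping the window and adjusting within it.

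The reply does not reach the independence problem, which is present whatever happens at 32 weeks.

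Two stronger readings are tempting:

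- A reader might infer that cord units stop at 32 weeks, so that every late transfusion is adult blood. Section 2 hints at this, but section 5.2 names the adult product as the one whose phase ends, and section 3.2 names both. The documents do not fix the direction.
- A reader might infer that the bias must be small because only a small late share fits the 1:1 ratio. That holds only if 1:1 is taken to apply before 32 weeks. Section 6.2 states it to 36 weeks, and a late share of 20% is compatible with it.

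**Conclusion.** The point holds in a limited form. The efficacy test ignores repeated transfusions within infants, so its standard errors are wrong in a direction that depends on how products are mixed within infants. Separately, the plan does not settle what changes at 32 weeks, and the test has no PMA term to protect against a change of mix.

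The resulting bias is zero if the mix is unchanged. Otherwise it is 0.05-0.20 SD for haematocrit rise across the illustrated scenarios, against a half-width of about 0.40 SD that itself assumes independence. Those figures rest on the assumed late share, the assumed early-late difference and all late transfusions being of one product. They are illustrations, not estimates. The documents support neither a direction nor a claim that the bias is large or small.

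The boundary problem concerns a secondary outcome; the primary outcome in section 2 is HbF at 32 weeks. Severity: minor.

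**What to change.** **Section 6.3.** Replace the plain Mann-Whitney test for haematocrit rise and transfusion interval with a model containing product, PMA at transfusion and an infant effect, for example a random intercept. Keep the 36-week window.

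**Sensitivity analysis.** Repeat the comparison on transfusions given up to completion of 32 weeks, following each interval to the next transfusion of any type so that intervals are not cut at the boundary. If late transfusions prove to be nearly all of one product, the PMA adjustment beyond 32 weeks rests on the assumed form of the PMA effect. The restricted analysis shows how much depends on that.

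**Wording.** Reconcile sections 2, 3.2, 3.5, 5.2 and 5.5 on what changes at 32 weeks, and state the period to which the 1:1 ratio in section 6.2 applies.

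**Cost.** No new samples or data are needed: section 5.9 already records PMA and the date and type of each transfusion. There is a little more analysis work, and the confidence intervals may be wider, but they would take account of the repeated transfusions. The restricted analysis is less precise: at f = 10% with 1:1 before 32 weeks, about 88 of 98 transfusions remain and the half-width goes from 0.40 to 0.42 SD, ignoring clustering. Adjusting for PMA does not remove other confounding from availability-based choice of product.

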4. TEST POPULATION

The study will include preterm infants who met the criteria of inclusion/exclusion and whose parents/tutors have given their informed consent. Based on the number of patients hospitalized every year in our NICU (roughly 150 patients/year) and the characteristics of the test population, we expect to achieve the sample size of 25 patients in 10 months.

4.1 Eligibility criteria

4.1.1 Inclusion criteria. All the patients who will be included in the study will have to meet the following inclusion criteria:

- Birth gestational age \leq 30 weeks and/or birth weight \leq 1000 grams;
- Need of transfusions before the 32nd week of PMA, according to the guidelines currently used by the NICU.

4.1.2 Exclusion criteria. None of the enrolled patients can be affected by one or more than one of the following pathologies:

- mother-fetus isoimmunization;
- hydrops fetalis;
- chromosomal anomalies and congenital malformations;
- acute hemorrhage at birth.

5. PROCEDURES

5.1 Enrollment. Cord blood donors will be enrolled according to the procedures implemented by the bank personnel of the UNICATT Cord Blood Bank. The medical personnel of the Neonatology ward will enroll patients when they are hospitalized in the NICU. The parents/tutors of the newborns who meet the inclusion criteria will be adequately informed about the study and will be asked to give their informed consent (Annex I and Annex I bis). Researchers will provide exhaustive information both on the aim of the study and the related procedures. Investigators will be in charge of providing all the necessary information, including that on the parents' right to withdraw their consent to participate in the study whenever they want and for whatever reason without affecting the newborn's treatment. A copy of the consent shall be provided to the parents/tutors and the researchers will keep another. Only the newborns whose parents have given their consent can be enrolled.

5.2 Enrollment communication to the Blood Transfusion Service. Once parents/tutors have given their informed consent, the researchers of the NICU will communicate the patient's

name to the Blood Transfusion Service. The researchers of the Blood Transfusion Service will keep an up-to-date list of the enrolled patients by reporting:

- date of the completion of the 32nd week of PMA (termination of A-RBC intervention phase);
- date of the completion of the 36th week of PMA (study termination).

5.3 Description of the blood component Umbilical Cord Blood red cell concentrates. The study will be based on the transfusion of umbilical cord blood units taken from the pregnant women who are part of the Cord Blood Bank donors and who gave their informed consent on the use of the donated unit for research purposes.

5.4 The collection of cord blood will be carried out in the birth centers that are part of the Cord Blood Bank, according to the procedures used by the Bank itself. The collected units will be adequately conserved at low temperatures (2-6°C) and fractionated within 24 hours. The units that are not eligible for transplant because of low cellularity (total nucleated cells <1,200 x 10⁶), with a volume >60 ml excluding the anticoagulant (CPD, Citrate, Phosphate, Dextrose), without clots and/or hemolysis, will be considered eligible for fractionation to obtain UCB-RBC. Eligible UCB units will be fractionated by an automatic blood component processing system (the UNICATT Cord Blood bankl will use Compomat[®] G4 by Fresenius HemoCare GmbH, D-61346, Bad Homburg, Germany). Red cell concentrates will be resuspended in a preservative solution containing adenosine, glucose and mannitol (SAGM, ratio red cell: SAGM = 2:1) and filtered with the filter Purecell[®] NEO Neonatal High Efficiency Leukocyte Reduction Filter (Pall, East Hills, NY, USA) to remove leukocytes. Blood cultures for bacteria and fungi will be set up. Only the units that tested microbiologically negative will be considered eligible for transfusion (blood cultures, molecular and serological tests for HCV, HBV, HIV and syphilis). UCB-RBC units will be stored at a temperature of 2-6°C for 14 days, in order to allow the γ -irradiation (¹³⁷Cs) when they are assigned to the patient.

5.5 Transfusion request. Units will be requested according to the procedures established by the Blood Transfusion Service, based on the current legislation and in accordance with the guidelines reported in Annex III. When a blood request arrives, the hematologist on duty at the Blood Transfusion Service will check if the patient's name is included among those enrolled in the study and the date of completion of the 32nd week of PMA; then he/ she will identify ABO-Rh(D) units to transfuse (UCB-RBC if available, otherwise A-RBC). The transfusion dose will be determined regardless of the type of blood component being used and will be established according to the criteria generally implemented in the NICU. The UCB-

RBC and A-RBC units will be transfused within six hours in order to reduce functional alterations of red cells and the risk of microbial contamination.

5.6 Monitoring of transfusion need. All the transfusions carried out in all the patients before the 36th week of PMA will be recorded. Before and after every transfusion, HbF, HbA and capillary arterial-blood gas will also be tested. Blood samples for CBC and/or reticulocytes will only be taken if clinically necessary and not for study-related reasons.

5.7 Monitoring of HbF and HbA levels. Three capillary blood samples will be taken every week for dosing HbF and HbA. If other tests for routine assistance, or for blood units cross-match, are carried out, part of the blood sample will be recovered for dosing HbF and HbA. The dosage will be carried out on samples that were stored at the Hematology Service of the Foundation, through HPLC on lysate samples. This procedure needs very low sample volumes (50-100 µL).

5.8 Definition of the prematurity-related pathologies (ROP, BPD, NEC and IVH). ROP (grade I-IV) will be diagnosed based on the criteria of the “International Committee for the Classification of Retinopathy of Prematurity” [49]; NEC will be diagnosed based on the criteria of Bell [50]; BPD is diagnosed when an infant continues to need additional oxygen after 28 days of age, at the 36th week of PMA [51]; the diagnosis of IVH will be based on the criteria of Papile [52].

5.9 Recording of clinical data and laboratory parameters. For each patient, the following parameters will be recorded on specific case report forms: GA and birth weight, sex, ethnicity, twin birth, PMA, respiratory support, additional oxygen, length of the hospitalization in the NICU, number of days under antibiotic therapy and PMA when leaving the hospital. All the causes of mortality and morbidity occurred within the 36th week of PMA will be recorded (infectious episodes, hemorrhagic events, kidney failure, thromboembolism, surgical complications, etc.). All the possible adverse events occurred within that date would also be recorded (for example, the unexpected adverse events, including all the alterations of the laboratory parameters, regardless of their seriousness). All the hematological (Hb, HbF% and HbA%, Hct) and transfusion data (date, number of transfusions, type of transfusion, volumes of transfused RBC) will also be recorded. For all those patients who were discharged before the completion of the 36th week of PMA, the clinical evaluation, the determination of HbF on capillary blood and the collection of data will be carried out at ambulatory level.

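### Adult red cells given before enrolment are neither barred nor adjusted for, so the unadjusted week-32 HbF comparison could be distorted in either direction

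*Combined protocol and SAP*

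**What the plan says.** **Eligibility.** Besides the gestational age or weight limit, 4.1.1 requires "Need of transfusions before the 32nd week of PMA, according to the guidelines currently used by the NICU". Section 4.1.2 opens with "None of the enrolled patients can be affected by one or more than one of the following pathologies" and lists isoimmunization, hydrops, chromosomal or congenital anomalies, and acute bleeding at birth. Earlier transfusion is not on the list.

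**Enrolment.** Under 5.1, "The medical personnel of the Neonatology ward will enroll patients when they are hospitalized in the NICU", and "Only the newborns whose parents have given their consent can be enrolled". No time limit is set relative to the first transfusion.

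**Access to cord blood.** After consent, the infant's name goes to the Blood Transfusion Service (5.2). On each request the hematologist on duty "will check if the patient's name is included among those enrolled in the study and the date of completion of the 32nd week of PMA" (5.5), then selects cord blood if it is in stock and adult cells if not.

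**Which transfusions count.** On recording, 5.6 says "All the transfusions carried out in all the patients before the 36th week of PMA will be recorded". The efficacy endpoint in 3.5 takes every transfusion up to week 36 and names no start. Section 3.2 begins the intervention phase at enrolment.

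**Analysis.** Section 6.3 compares HbF between transfusion types univariately (Mann-Whitney, Kruskal-Wallis) and tests transfusion type against morbidity with Fisher's exact test. Neither uses baseline HbF or earlier adult exposure. Section 6.2 assumes that "for every adult red cell transfusion, HbF will be reduced by 15-20% compared to the pre-transfusion values".

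**The concern.** The study is not randomized. Its product comparison is most credible if the product an infant receives depends on cord blood stock and not on the infant. A unit given before the infant is listed lies outside the study's stock-based choice, and its adult hemoglobin remains in the circulation when study transfusions begin. If such infants are enrolled, part of any week-32 HbF difference between products could reflect what they received before the study could choose a product. The planned test cannot separate the two. An infant with an earlier adult unit could also be counted as exposed only to cord blood if just the study transfusions were considered.

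**Working it through.** **1. The text, step by step.** Consent precedes listing (5.1, 5.2), and listing precedes the study's product choice (5.5). A unit given before listing is therefore outside the study's cord blood route. Section 4.1 does not keep the infant out, 3.5 gives no start date that would keep the unit out, and 6.3 has no term that would allow for it.

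**2. The plan's counts (6.2).** 25 infants × 8 weeks = 200 infant-weeks. 200 − 2 × 1.9 = 196.2, which gives the stated 196. 196 / 8 = 24.5 infants, and 24.5 × 4 = 98 transfusions. At 1:1 this is 49 UCB-RBC and 49 A-RBC. The counts reproduce.

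**3. Size per infant.** Inputs from 6.2: HbF at birth 85-90%; relative fall per adult unit 15-20%.
- Smallest loss: 85 × 0.15 = 12.75 points. Largest: 90 × 0.20 = 18 points.
- HbF after one unit: 85 × 0.80 = 68.0% to 90 × 0.85 = 76.5%.
- For scale, the plan's expected fall from birth to week 36 without transfusion is 85 − 75 = 10 to 90 − 70 = 20 points.

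Later adult units shrink this gap in proportion. After two of them (four transfusions at 1:1) it is 12.75 × 0.85² = 9.2 to 18 × 0.80² = 11.5 points, ignoring natural decline.

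If 15-20% is read as percentage points, the loss is 15-20 points and HbF after one unit is 65-75%.

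**4. Size and sign in the comparison.** Let p_A and p_U be the shares of infants with one pre-enrolment adult unit among those later compared as A-RBC and as UCB-RBC. The difference in mean HbF at enrolment from this source is (p_A − p_U) × 12.75 to 18 points. Neither share is in the documents, so these are assumed values:
- difference 0: no shift
- 0.10: 1.3 to 1.8 points
- 0.20: 2.6 to 3.6 points
- 0.40: 5.1 to 7.2 points

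A positive difference favours UCB-RBC, and a negative one counts against it.

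**5. Precision lost by starting the contrasts at enrolment.** At 49 v 49, a standardized difference of 0.6 (the smaller of the two targets in 6.3) and two-sided 0.05, power = Φ(0.6 × √(49/2) − 1.96) = Φ(1.01) = 84%. With Mann-Whitney efficiency 0.955 it is 83%. Now suppose a share f of the 24.5 infants each had one pre-enrolment unit, counted among the 49 A-RBC. Removing these leaves n_A = 49 − 24.5f, and power = Φ(0.6 / √(1/n_A + 1/49) − 1.96).

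| f (assumed) | Units removed | A-RBC left | Power | Power, Mann-Whitney |
|---|---|---|---|---|
| 10% | 2.5 | 46.5 | 83% | 82% |
| 25% | 6.1 | 42.9 | 82% | 80% |
| 50% | 12.2 | 36.8 | 79% | 77% |
| 100% | 24.5 | 24.5 | 68% | 66% |

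These figures treat transfusions as independent, although several come from the same infant. They show only the relative loss, which is small unless about half the infants are affected.

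**The case against.** The strongest reply is that the plan expects enrolment first and transfusion afterwards. Section 5.1 enrols during the NICU stay, 3.2 starts the intervention at enrolment, and the Enrolled set in 6.1 includes infants who are never transfused. Section 5.6 asks for HbF before and after every transfusion, which is a study procedure and suggests infants already enrolled. On that reading the affected group may be empty.

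A reader might infer that the plan analyses pre-enrolment units as A-RBC. No section says so: 5.6 is about recording, and the count from birth in 6.2 is a planning rate. A reader might also infer that the sickest infants are bound to be adult-exposed, so that the bias favours cord blood. The documents give no consent delay, no timing of first transfusion and no link to severity. Excluding acute bleeding at birth removes one cause of very early transfusion. An infant who later receives only cord blood starts from diluted HbF, which works the other way.

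It is also fair that, at about four transfusions and a 1:1 ratio, infants average two adult units each. Mixed exposure and carry-over are thus general features of the design, and pre-enrolment units are at most a subset. Nor can those units simply be dropped from the morbidity contrast, since an adult-exposed infant could then be classed as cord-only.

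All of this limits the claim. It does not supply a start date in 3.5, a bar in 4.1 or a baseline term in 6.3. A clarifying sentence on eligibility would help, but would not adjust the comparison for infants who do enter with lowered HbF.

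**Conclusion.** The point holds as a gap in the analysis plan. An infant given adult cells before enrolment may enter, and would do so with HbF lower by 12.75-18 points per unit, taking the plan's relative fall from its birth values. The primary comparison makes no allowance for this. The effect on the group comparison depends on how unevenly such infants fall between products, which the documents do not give. It could be nil or several points, in either direction. The number affected is unknown and may be zero, and an excess of severe cases among them is possible but not shown. The remedy is still worthwhile, because the comparison is non-randomized and unadjusted and the HbF measurements needed are already planned.

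**What to change.** - **Baseline (6.3).** Define baseline as the first HbF at or after enrolment and before the first study transfusion. Compare week-32 HbF between products in a model adjusted for it, keeping the Mann-Whitney test as supportive.
- **Start of the contrasts (3.5, 6.3).** State that the UCB-RBC v A-RBC contrasts for HbF and for transfusion efficacy begin at enrolment.
- **Earlier adult units.** Flag them on the case report form. In the morbidity analysis, carry them as prior adult exposure and do not delete them, so that no exposed infant is classed as UCB-only.
- **Sensitivity analysis.** Repeat the primary comparison without infants transfused before enrolment.

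Transfusion dates and types (5.9), HbF around each transfusion (5.6) and three HbF samples a week (5.7) are already planned, so no extra sampling is needed. The costs are one flag, a model in place of a rank test as the main analysis, one covariate in a sample of 25, slightly fewer A-RBC transfusions in the contrasts, and a smaller sample in the sensitivity analysis. If no infant was transfused before enrolment, no transfusion or infant is lost and the covariate is the only statistical cost.
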